7.5. Preparation/Handling/Storage/Accountability

Abemaciclib will be supplied by Lilly as tablets/capsules for oral administration. Abemaciclib tablets/capsules should be stored according to the temperature range listed on the product label and should not be opened, crushed, or chewed. Patients should store the abemaciclib tablets/capsules in the original package provided and be instructed to keep all medication out of reach of children.

7.6. Treatment Compliance

Patient compliance with study medication and completion of patient e-diary will be assessed at each visit. Compliance will be assessed by counting returned tablets/capsules and e-diary review. The e-diary will be supplied by Lilly. Deviations from the prescribed dosage regimen should be recorded on the case report form (CRF). Patients who are deemed noncompliant will

receive additional training, as required, and the importance of compliance with the protocol will be reinforced.

Patients who are significantly noncompliant with abemaciclib and administration conditions may be discontinued from abemaciclib treatment after discussion/consultation with the Lilly CRP. A patient will be considered noncompliant or if she/he misses more than 25% of abemaciclib doses during the first 3 cycles of treatment. Similarly, a patient will be considered significantly noncompliant if she or he is judged by the investigator to have intentionally or repeatedly taken more than ($\geq 125\%$) the prescribed amount of medication. Abemaciclib dose suspensions or delays related to toxicity may occur and will not result in a patient being considered as noncompliant.

7.7. Concomitant Therapy

Appropriate documentation of all forms of premedications, supportive care, concomitant medications, and supplements must be captured at each visit in the CRF. Concomitant medications and supportive care therapies must also be documented at the time of discontinuation and at the short-term follow-up visit.

No other anticancer therapy will be permitted while patients are on study treatment. Of note, megestrol acetate as an appetite stimulant is permitted.

Concurrent treatment with standard-of-care bone-modifying agents (such as bisphosphonates or receptor activator of nuclear factor kappa B ligand [RANKL]-targeting agents) is permitted.

Abemaciclib is extensively metabolized through oxidation by cytochrome P450 (CYP)3A. In clinical drug interaction studies, coadministration of clarithromycin, a strong CYP3A inhibitor, increased exposure (AUC) to abemaciclib by 3.4-fold (Study I3Y-MC-JPBE) and coadministration of rifampin, a strong CYP3A inducer, decreased exposure to abemaciclib by 95% (Study I3Y-MC-JPBF). Therefore, grapefruit or grapefruit juice as well as inducers and inhibitors of CYP3A should be substituted or avoided if possible ([Appendix 6](#)).

All patients may receive supportive therapy with dexamethasone, preferably ≤ 7 days, if clinically indicated. Patients requiring more than 7 days of dexamethasone therapy will not incur a protocol deviation.

Abemaciclib can be coadministered with drugs which are substrates of CYP enzymes.

Abemaciclib and/or its major metabolites inhibit the efflux transporters P-glycoprotein and breast cancer resistance protein and renal transporters organic cation transporter 2, multidrug and toxin extrusion protein 1 (MATE1) and MATE2-K at clinically relevant concentrations. Therefore, substrates of these transporters such as metformin and those with a narrow therapeutic index such as digoxin and dofetilide should be substituted or avoided if possible.

No other chemotherapy, immunotherapy, cancer-related hormone therapy, experimental drugs, or herbal supplements intended to treat cancer will be permitted while the patients are on this study.

Palliative radiation therapy is permitted after discussion with and agreement of the Lilly CRP or designee for irradiating small areas of painful metastases that cannot be managed adequately using systemic or local analgesics. Such areas must not be an identified target lesion if Response Evaluation Criteria in Solid Tumors (RECIST) v1.1 is used to measure disease and must not constitute progressive disease or meet RECIST criteria for progressive disease. Any symptomatic deterioration or clinical disease progression requiring, in the opinion of the investigator, other forms of specific antitumor systemic therapy, will be cause for discontinuation of study therapy.

In addition, any disease progression requiring other forms of specific antitumor therapy will also necessitate early discontinuation from the study. Appropriate documentation for all forms of premedications, supportive care, and concomitant medications must be captured on the case report form.

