7.2.1. Selection and Timing of Doses

During the on-study treatment period (primary outcome phase and extension phase), a delay of study treatment due to holiday, weekend, inclement weather, or other unforeseen circumstances will be permitted for a maximum of 7 consecutive days and not counted as a protocol deviation. In exceptional cases, for planned delays (including, but not limited to vacation or holidays), additional study treatment may be dispensed. In these cases, patients should return to the original visit schedule calculated from Day 1.

For each study arm, abemaciclib will be administered orally at 200 mg BID, with at least 6 hours separating doses on a continuous schedule and as assigned by administration conditions for each study arm. Details on treatment administration are described in Section 7.1. Treatment with abemaciclib will be given until evidence of disease recurrence or other discontinuation criteria are met (see Section 8).

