7.4. Dose Modification

7.4.1. Special Treatment Considerations of Adverse Events of Special Interest

Table JPCP.7.2 presents dose adjustments to occur IF the event was related to abemaciclib. Any questions related to **dose adjustments** may be discussed with Lilly CRP.

Table JPCP.7.2. Dose Adjustments for Treatment-Emergent, Related*, and Clinically Significant Adverse Events of Abemaciclib

Toxicity Type	Toxicity Profile and Severity	Dose Suspension	Dose Reduction
Hematologic Toxicity	Grade 3	Dose MUST be suspended until toxicity resolves to at least Grade 2.	Dose reduction is NOT required.
Hematologic Toxicity	Recurrent ^a Grade 3	Dose MUST be suspended until toxicity resolves to at least Grade 2.	Dose MUST be reduced by 1 dose level.
Hematologic Toxicity	Grade 4	Dose MUST be suspended until toxicity resolves to at least Grade 2.	Dose MUST be reduced by 1 dose level.
Hematologic Toxicity: If patient requires administration of blood cell growth factors	Regardless of severity (Use of growth factors according to ASCO Guidelines)	Dose MUST be suspended for at least 48 hours after the last dose of blood cell growth factors was administered and until toxicity resolves to at least Grade 2.	Dose MUST be reduced by 1 dose level unless already performed for incidence of toxicity that led to the use of growth factor.
Non-Hematologic Toxicity ^b (except diarrhea, ALT increased, and ILD/pneumonitis)	Persistent or recurrent Grade 2 that does not resolve with maximal supportive measures within 7 days to baseline or Grade 1.	Dose MUST be suspended until toxicity resolves to either baseline or Grade 1.	Dose MUST be reduced by 1 dose level.
Non-Hematologic Toxicity ^b (except diarrhea, ALT increased, and ILD/pneumonitis)	Grade 3 and 4	Dose MUST be suspended until toxicity resolves to either baseline or Grade 1.	Dose MUST be reduced by 1 dose level.
Diarrhea	Grade 2 that does not resolve within 24 hours to at least Grade 1	Dose MUST be suspended until toxicity resolves to at least Grade 1.	Dose reduction is NOT required.
Diarrhea	Persistent or recurrent Grade 2 that does not resolve with maximal supportive measures, or any Grade of diarrhea that requires hospitalization	Dose MUST be suspended until toxicity resolves to at least Grade 1.	Dose MUST be reduced by 1 dose level.
Diarrhea	Grade 3 or 4	Dose MUST be suspended until toxicity resolves to at least Grade 1.	Dose MUST be reduced by 1 dose level.

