7.4.1.1. Dose Adjustments of Abemaciclib

Dose adjustments as outlined in Table JPCP.7.3 are allowed. Abemaciclib must be reduced sequentially by 1 dose level.

For patients requiring dose reduction(s), any re-escalation to a prior dose level is permitted only after consultation with the Lilly CRP. After re-escalation, subsequent dose adjustments should be based on the dose of abemaciclib that the patient is currently receiving.

Table JPCP.7.3. Dose Adjustments of Abemaciclib

Dose Adjustment	Oral Dose	Frequency
0	200 mg	Twice daily with at least 6 hours between doses
1	150 mg	Twice daily with at least 6 hours between doses
2	100 mg	Twice daily with at least 6 hours between doses
3	50 mg	Twice daily with at least 6 hours between doses

If a patient receiving the 50-mg BID dose of abemaciclib requires further dose reduction, the patient must be discontinued from study treatment.

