Appendix 6. Protocol JPCP Inducers and Inhibitors of CYP3A

The information in this table is provided for guidance to investigators and does not preclude the use of these medications if clinically indicated.

Strong Inducers of CYP3A

Carbamazepine
Dexamethasone^a
Phenobarbital/phenobarbitone
Phenytoin
Rifapentine
Rifampin
Rifabutin
St John's wort

Moderate Inducers of CYP3A

Bosentan
Lenisurad
Modafinil
Primidone
Telotristat ethyl

Strong Inhibitors of CYP3A

Aprepitant
Ciprofloxacin
Clarithromycin
Conivaptan
Diltiazem
Erythromycin
Fluconazole
Itraconazole
Ketoconazole
Nefazodone
Posaconazole
Troleandomycin
Verapamil

^a Important note: All patients may receive supportive therapy with dexamethasone, preferably ≤ 7 days, if clinically indicated

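### Before an unavoidable strong CYP3A inhibitor is given, the protocol requires no hold, lower dose or sponsor consultation; 200 mg BID stays the default

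*Protocol*

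**What the plan says.** Protocol section 7.7 reports that clarithromycin, a strong CYP3A inhibitor, "increased exposure (AUC) to abemaciclib by 3.4-fold". Its instruction to sites is that "inducers and inhibitors of CYP3A should be substituted or avoided if possible". Appendix 6 names 13 strong inhibitors, among them "Clarithromycin" and "Ciprofloxacin", and adds that the list "does not preclude the use of these medications if clinically indicated". Co-administration is therefore discouraged but permitted.

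Four other places govern the dose:

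- **Section 7.2.1:** "For each study arm, abemaciclib will be administered orally at 200 mg BID". It makes no exception for co-medication.
- **Section 7.4.1:** Table JPCP.7.2 "presents dose adjustments to occur IF the event was related to abemaciclib". Inhibitor use is not a trigger. Questions about dose adjustment may be taken to the sponsor physician.
- **Section 7.4.1.1:** "Abemaciclib must be reduced sequentially by 1 dose level". The levels are 200, 150, 100 and 50 mg BID. A patient on 50 mg who needs a further reduction must stop study treatment.
- **Section 8.1:** after three reductions, an adverse event that would call for a fourth ends treatment.

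No exclusion criterion mentions CYP3A inhibitors. The wash-out table in inclusion criterion 7 covers prior cancer treatments and major surgery.

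**The concern.** The protocol states a large interaction and permits the drugs that may cause it, but it does not say what must be done with the abemaciclib dose. A site that follows the text may give 200 mg BID alongside a permitted strong inhibitor. If it decides to reduce, the one-level rule keeps it from going straight to a dose near the intended exposure.

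The stake is patient safety. Section 5.5 ties this study's 200 mg monotherapy setting to the prior study with the most diarrhea, overall and at Grade 3. Avoidable overexposure adds to a known toxicity, and the resulting events may be counted in the primary endpoints.

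The protocol does write such rules for other interventions. Growth factors carry a mandatory hold and a one-level reduction. Palliative radiation requires a hold and the sponsor physician's agreement. Major surgery carries a recommended hold. Strong CYP3A inhibitors, with a reported multiple-fold exposure effect, carry none of these.

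**Working it through.** **Inputs**

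- AUC factor with clarithromycin: 3.4 (Protocol 7.7). This is a cited result from a separate interaction study and cannot be re-derived from the documents.
- Dose levels: 200, 150, 100 and 50 mg BID (Table JPCP.7.3).
- Assumption: abemaciclib AUC is proportional to dose.

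**Exposure relative to 200 mg BID without an inhibitor** = dose × 3.4 / 200

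| Dose BID | Calculation | Relative AUC |
|---|---|---|
| 200 mg | 200 × 3.4 / 200 | 3.40 |
| 150 mg | 150 × 3.4 / 200 | 2.55 |
| 100 mg | 100 × 3.4 / 200 | 1.70 |
| 50 mg | 50 × 3.4 / 200 | 0.85 |

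**Dose that matches the intended exposure** = 200 / 3.4 = 58.8 mg BID. The nearest available level is 50 mg, three steps below the start.

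**Alternative reading of the figure.** If the wording means an increase by 3.4 times, that is to 4.4 times, the relative AUC is 4.40, 3.30, 2.20 and 1.10 at the four levels. The matching dose is then 200 / 4.4 = 45.5 mg. The nearest level is again 50 mg.

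**The other 12 listed drugs.** The documents give no factor for them, so I assume 1.0 to 3.4. The largest factor that each level offsets is 200 / dose:

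- 150 mg: 200 / 150 = 1.33
- 100 mg: 200 / 100 = 2.0
- 50 mg: 200 / 50 = 4.0

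At a factor of 1.0 no change is needed. Up to 1.33 one step is enough, up to 2.0 two steps, and above that three.

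**Is anything required before co-administration?** Section 7.7 gives only the substitute-or-avoid instruction. Table JPCP.7.2 acts after a related adverse event. Section 7.4.1.1 allows adjustments but fixes the step size. Section 7.4.1.2 permits suspension, and 7.4.1 permits discussion. None of these requires a step when a listed inhibitor is started.

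**The case against.** The strongest reply is that a careful site already has what it needs. Section 7.4.1.2 opens with a general permission to suspend or delay, and toxicity comes in only in the next sentence. Section 7.4.1.1 does not demand an adverse event before each step, sets no waiting time between steps, and allows re-escalation after consulting the sponsor physician. Section 5.5 leaves it to the physician to judge whether a patient suits 200 mg. All of this stands, and it narrows the point: a hold or consultation is available but optional, and no passage lifts the one-level rule for this case.

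A reader might infer more than the documents support:

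- **That the protocol compels 200 mg with an inhibitor until toxicity occurs.** It does not, for the reasons just given.
- **That such a patient will use up all three reductions and lose treatment.** That needs an inhibitor as strong as clarithromycin, continued through successive events despite the instruction to avoid it. Mandatory holds also interrupt the sequence: Grade 2 diarrhea not resolved within 24 hours, and any Grade 3 or 4 diarrhea, stop dosing until resolution to Grade 1 or better.
- **That the diarrhea guidance forces a listed drug on patients.** Section 7.7.1.1 requires broad-spectrum antibiotics in severe or complicated cases and gives fluoroquinolones as an example. Ciprofloxacin is listed, but the agent is left open and 7.7 says to substitute where possible.
- **That inhibitor use could rival the food effect.** The 9% food effect on AUC is for abemaciclib and its active metabolites, whereas the 3.4-fold figure is stated for abemaciclib. The two are not like for like.

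The amendment summary says that 7.7 was aligned with the Investigator's Brochure and that Appendix 6 followed 7.7. Sites may hold dose advice there or in the label. This cannot be checked from the documents, and the protocol's dose sections do not point there for this purpose.

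**Conclusion.** The point holds as a safety gap in a narrow case. When a listed strong inhibitor is clinically indicated, the protocol permits it and requires no hold, lower dose or sponsor consultation first, and any reduction must go one level at a time. For clarithromycin, one step down leaves 2.55 times the intended parent exposure, and only the 50 mg level comes close to it.

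This size rests on exposure proportional to dose and on a figure reported for one drug. The effect on active metabolites is not given, so the net effect may be smaller. The effect of the other 12 drugs is unknown, and the number of patients affected cannot be estimated. A reader might also infer a biased comparison of the meal conditions. The documents do not support that: randomization balances inhibitor use in expectation. This is a cheap improvement for patient safety and does not challenge the analysis.

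**What to change.** Add to Protocol 7.7, for any indication:

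> If a strong CYP3A inhibitor is unavoidable, the investigator must agree an abemaciclib hold or a lower dose level with the sponsor physician before co-administration. The one-level rule in 7.4.1.1 does not apply to this change, and it does not count toward the 3 reductions in 8.1. The prior dose is resumed after the inhibitor has been stopped and washed out. If toxicity occurs at 50 mg BID during co-administration, hold abemaciclib until the inhibitor is stopped; the 50 mg discontinuation rule in 7.4.1.1 does not apply. Record the reason as concomitant medication.

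The text names no fixed dose because only clarithromycin has a figure. The sentence on 50 mg is needed: without it, a patient moved there in advance would have no reduction left. SAP 5.8 needs no change, because it already counts only reductions, interruptions and discontinuations due to diarrhea.

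The cost is a short amendment and one reason code on the dosing form. Any such patient would be off 200 mg for part of the primary outcome phase. The dose levels are already in Table JPCP.7.3, and baseline and concomitant medications are already collected.

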7.7.1. Supportive Care

Patients should receive full supportive care to maximize quality of life (for example, antiemetics or standard of care bone-modifying agents). Patients will receive supportive care based on the judgment of the treating physician. If it is unclear whether a therapy should be regarded as supportive care, the investigator should consult the Lilly CRP. Use of any supportive care therapy should be reported in the CRF.

Guidelines regarding the use of other specific supportive care agents are presented below.

7.7.1.1. Supportive Management for Diarrhea

Patients should receive instructions on the management of diarrhea and prescribed antidiarrheal therapy (protocol recommended loperamide) on Day 1. The antidiarrheal agent, loperamide is not for prophylactic use, and should only be used in the event of diarrhea. Loperamide will be supplied or reimbursed by the sponsor according to local laws. In the event of diarrhea, provided loperamide antidiarrheal therapy should be initiated as early as possible and the site should follow the guidance below:

- At the first sign of loose stools, the patient should initiate loperamide antidiarrheal therapy, if not already receiving such therapy, and notify the investigator/site for further instructions and appropriate follow-up.
- Patients should also be encouraged to drink fluids (for example, 8 to 10 glasses of clear liquids per day).
- Site personnel should assess response within 24 hours.
- If diarrhea does not resolve with loperamide therapy within 24 hours to either baseline or Grade 1, abemaciclib should be suspended until diarrhea is resolved to baseline or Grade 1.
- When abemaciclib recommences, dosing should be adjusted as outlined in [Table JPCP.7.2](#) and [Section 7.4.1.1](#).

In cases of significant diarrhea, Grades 2 through 4 ([Appendix 7](#)), that have not responded to interventions as outlined above, if the investigators are considering the addition of steroids to treat potential colitis, the sponsor strongly recommends an endoscopic procedure to document colitis prior to initiating steroids.

In cases of severe diarrhea, the measuring of neutrophil counts and body temperature and proactive management of diarrhea with antidiarrheal agents should be considered.

If diarrhea is severe (requiring intravenous [IV] rehydration) and/or associated with fever or severe neutropenia, broad-spectrum antibiotics such as fluoroquinolones must be prescribed.

Patients with severe diarrhea or any grade of diarrhea associated with severe nausea or vomiting should be carefully monitored and given IV fluid (IV hydration) and electrolyte replacement.

7.7.1.2. Therapy for Febrile Neutropenia

Patients experiencing febrile neutropenia, especially with diarrhea or dyspnea, should be managed in a hospital setting according to standard procedures, with the urgent initiation of IV antibiotic therapy. Events that require a patient to be hospitalized are considered SAEs (see [Section 9.2.1](#)).

7.7.1.3. Growth Factor Therapy

Growth factors should not be administered to a patient to satisfy study inclusion criteria.

Growth factors may be administered in accordance with ASCO guidelines (Smith et al. 2015). Dosing of abemaciclib must be suspended if the administration of growth factors is required and must not be recommenced within 48 hours of the last dose of growth factors having been administered. Following the administration of growth factors, the dose of abemaciclib must be reduced by 1 dose level on recommencement, if a dose reduction for the specific event necessitating the use of the growth factors has not already occurred.

7.8. Treatment after the End of the Study

Not applicable.

[figure not shown]
7.8.1. Treatment after Study Completion

Study completion will occur when the last enrolled patient completes up to Cycle 4 Day 1. Investigators will continue to follow the Schedule of Activities ([Section 2](#)) for all patients until notified by Lilly that study completion has occurred.

7.8.1.1. Continued Access

The continued-access period will apply to this study only if at least 1 patient is still on abemaciclib when study completion occurs.

Patients who are still on abemaciclib at the time of study completion may continue to receive abemaciclib in the continued-access period if they are experiencing clinical benefit and no undue risks.

^a Lilly will notify sites when study completion occurs.

^b End of study occurs at the last visit or last scheduled procedure for the last patient.

Figure JPCP.7.1. Continued-access diagram.

8. Discontinuation Criteria

8.1. Discontinuation from Study Treatment

Patients will be discontinued from study treatment in the following circumstances:

- the patient is treated in any other clinical study involving an investigational product or enrolled into any other type of medical research judged not to be scientifically or medically compatible with this study
- the patient becomes pregnant during the study
- the patient is significantly noncompliant with study procedures and/or treatment as described in Section 7.6
- the patient has evidence of disease progression
- the patient experiences unacceptable toxicity
- the patient has had 3 dose reductions and experiences an AE that would cause a fourth dose reduction
- the patient, for any reason, requires treatment with another therapeutic agent that has been demonstrated to be effective for treatment of the study indication. Discontinuation from abemaciclib will occur prior to introduction of the new agent
- the investigator decides that the patient should be discontinued from abemaciclib
- the patient requests to be discontinued from abemaciclib.

Patients who are discontinued from abemaciclib will have follow-up procedures performed as shown in the Schedule of Activities (Section 2).

